5.1 INCLUSION CRITERIA

Patients are eligible to be included in the study only if all the following criteria are met:

- 1. Male and female adults 18 to 70 years of age (inclusive) at the time of informed consent.
- 2. Diagnosed with mild to moderate AD, meeting at least 3 major and 3 minor criteria according to Hanifin and Rajka (Hanifin 1980; Appendix 4, Section 10.4.4) prior to or at the Screening visit.
- 3. History of AD for at least 6 months as determined by the Investigator through patient interview.
- 4. Stable disease for the 4 weeks prior to the screening visit with no significant flares in AD as determined by the Investigator.
- 5. Validated Investigator Global Assessment-atopic dermatitis (vIGA-AD) score of Moderate (3) or Mild (2) at Screening. The vIGA-AD is evaluated for the entire body except scalp, palms, soles and genitals.
- 6. Has AD involvement (excluding scalp, palms, soles and genitals) of at least 1.0% BSA and no more than 14.0% BSA.
- 7. Has at least two target lesions 100 cm² or greater with a difference no greater than 1 point in lesion TSS and at least 5 cm apart located on the trunk (excluding genitals) or upper extremities (excluding palms)
- 8. Male patients are eligible to participate if they agree to the following during the intervention period and for at least 2 days (eg, 5 terminal half-lives) after the last dose of study intervention,
- Refrain from donating sperm

PLUS, either:

- Be abstinent from heterosexual intercourse as their preferred and usual lifestyle (abstinent on a long term and persistent basis) and agree to remain abstinent.

OR

Must agree to use contraception/barrier as detailed below:
 Agree to use a male condom and an additional highly effective contraceptive method as described in Appendix 2 Contraceptive and barrier guidance (Section 10.2) when

having sexual intercourse with a woman of childbearing potential (WOCBP) who is not currently pregnant.

- 9. A female patient is eligible to participate if she is not pregnant or breastfeeding, and one of the following conditions applies:
- Is a WONCBP as defined in Appendix 2 Contraceptive and barrier guidance (Section 10.2).

OR

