1 INTRODUCTION

1.1 STUDY DESIGN

PRN473 is also known as SAR444727 and both terminologies are used in an interchangeable way in this document. For the reporting “SAR444727” will be used.

Study ACT17131 is a Phase 2a that consists of a randomized, double-blind, intra-patient placebo-controlled treatment period and an open-label uncontrolled treatment period.

The objective of the study is to evaluate the safety, tolerability, pharmacokinetics (PK) and preliminary efficacy of topically administered SAR444727 in up to 40 participants with mild to moderate atopic dermatitis (AD).

On Day 1 (Baseline) of the Blinded Period, 2 target lesions of 100 cm² area each with a difference no greater than 1 point in lesional Total Sign Score (TSS) are randomly assigned to treatment in an intra-participant 1:1 manner, with one lesion assigned to SAR444727 Gel 5% and the other to matching placebo (ie, same inactive ingredients). SAR444727 Gel 5% and matching placebo (ie, same inactive ingredients) are applied twice a day (BID, morning and evening) at a quantity of 2.5 mg/cm² to a 100 cm² area of each target lesion on Days 1-14 (Blinded Period). On Days 15-42 (Open-Label Period), participants are instructed to apply SAR444727 Gel, 5% BID to all AD-affected areas in a thin layer (excluding the scalp, palms, soles and genitals), and should continue to treat the assigned areas throughout the Open-label Period.

Participation will take approximately 13 weeks, including up to a 5-week screening period, a 6-week treatment period (2-week blinded and 4-week open label), end of study assessments 1 day after last dose, and a safety follow-up phone call 2 weeks after last dose.

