3.4 TERTIARY/EXPLORATORY ENDPOINT(S) ANALYSIS

There are two type of exploratory endpoints. The first exploratory endpoint is biomarker to evaluate changes in blood samples, skin tape stripplings, and skin biopsies. Details are given in [Section 3.7.1.2](#).

The second exploratory endpoints are efficacy endpoints during double-blind period and Open-label period based on the efficacy population. For the double-blind period, treatment differences or ratios will be assessed for SAR444727 Gel, 5% versus placebo at Day 8 and Day 15, and data will be presented by treatment for the blinded period, for scores assessed per lesion, and overall otherwise. During the Open-Label Period, efficacy will be assessed mainly at Days 29 and 43,

overall. For TSS, data will be described over the full course of the study presented by treatment received during the double-blind Period.

More specifically, the following endpoints will be assessed:

During double-blind period

- Change from Baseline in lesional TSS for the 2 target lesions at Day 8 and Day 15
- Change from Baseline in daily lesional Peak Pruritus Numeric Rating Scale (PP-NRS) score for the 2 target lesions up to Day 15 and at Day 15
- Change from Baseline in lesional validated Investigator Global Assessment for AD (v-IGA-AD) score for the 2 target lesions at Days 8 and 15
- Lesional v-IGA-AD response (proportion of participants with a lesional v-IGA-AD score of 0 [clear] or 1 [almost clear] and ≥ 2 -grade improvement from Baseline) at Days 8 and 15

During Open-label period

- For lesional TSS
 - Change from Baseline in lesional TSS for the 2 target lesions at Days 29 and 43
 - Change from Day 15 in lesional TSS for the 2 target lesions at Days 29 and 43
- For PP-NRS
 - Change in daily global PP-NRS from Day 15 to Days 29 and 43
 - Change in weekly average of PP-NRS from Day 15 to Days 29 and 43
 - Proportion of participants achieving at least 3-point reduction from Day 15 in daily global PP-NRS at Days 29 and 43 in participants with PP-NRS ≥ 3 at Day 15
 - Proportion of participants achieving at least a 4-point reduction from Day 15 in daily global PP-NRS at Days 29 and 43 in participants with PP-NRS ≥ 4 at Day 15
- For Eczema Area and Skin Severity Index (EASI)
 - Percent change from Baseline in EASI at Days 29 and 43
 - Percent change from Day 15 in EASI at Days 29 and 43

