For the intra-participant comparison of SAR444727 vs placebo during the double blind period, binary endpoints (only for lesional v-IGA-AD response) will be analyzed for Day 8 and Day 15 separately, using a logistic regression model with intervention (SAR444727, placebo) as fixed effects. Odds ratio and difference in proportions as well as the corresponding 95% CI will be provided.

Analyses for continuous endpoints

The descriptive statistics (mean, SD, SEM, median, Q1, Q3, and range) for all continuous endpoints collected will be provided by treatment and time point on raw data, absolute changes or percent changes from baseline using the baseline efficacy population. Boxplots will also be provided by treatment and time point. Absolute or percent change from baseline and ratio from Baseline (mean \pm SEM and/or median with interquartile range) will also be produced by treatment for the double blind period.

For the intra-participant comparison of SAR444727 vs placebo, a linear mixed model (using restricted maximum likelihood) with repeated measurements will be fitted to estimate the difference in mean change in lesional TSS from Baseline to Day 15; and from Baseline to Day 8.

In addition to the visit, treatment, and visit-by-treatment interaction terms, the model includes the participant-specific baseline lesional TSS score covariate. Repeated measurements for visit are taken within participant and an unstructured covariance matrix will be used to model the within-subject variance-covariance errors. Baseline lesional TSS will be defined as the mean TSS from the two treated lesions at Baseline.

Change from baseline TSS= Intercept + TSS_{base} + VISIT + TRT + VISIT*TRT + Error

Least square means will be calculated for change from Baseline to Day15 for both treatments and differences of means for SAR444727 versus placebo with two-sided 95% CI will be derived from the model framework.

The model may be simplified if there are convergence issues.

SAS Statement

```
proc mixed data= method=reml;
  class VISITNUM USUBJID TRT;
  model CHGSC=BASESC TRT VISITNUM TRT*VISITNUM/solution ddfm=kr ;
  repeated VISITNUM*TRT/type=UN subject=USUBJID;
  lsmeans VISITNUM*TRT /slice=VISITNUM cl;
  estimate "SAR versus Plbo D15" TRT -1 1 VISITNUM*TRT 0 0 -1 1 /cl;
  estimate "SAR versus Plbo D8" TRT -1 1 VISITNUM*TRT -1 1 0 0 /cl;
run;
```

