3.8 INTERIM ANALYSES

An interim analysis (IA) for internal decision making will be implemented when approximately 25 or more of the planned participants have completed the Blinded Period (Day 15). Available data of the Open Label Period may be included in the analysis as appropriate.

The outcome is meant for internal decision making and may lead to early termination of the study only in case of unfavorable signals, or continuation without any changes.

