4 SAMPLE SIZE DETERMINATION

No sample size calculations were performed due to the exploratory nature of this study.

The sample size of up to 40 for this study with participants receiving both SAR444727Gel, 5% and placebo is based upon empirical clinical consideration. The sample size is considered adequate to evaluate the safety, tolerability, and PK of topically administered SAR444727.

This study is signal seeking and neither aimed nor powered to provide formal inferential statistical analyses.

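### The logistic odds ratio planned for lesional vIGA-AD response does not exist if no placebo lesion responds, and the SAP has no fallback for that case

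*SAP*

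**What the plan says.** Each participant has one lesion on active gel and one on placebo. In SAP section 3.4, lesional vIGA-AD response is the only binary endpoint compared between the two lesions. It is analysed at Day 8 and Day 15 separately, "using a logistic regression model with intervention (SAR444727, placebo) as fixed effects", and the SAP then commits to results: "Odds ratio and difference in proportions as well as the corresponding 95% CI will be provided".

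The SAP does not say how the model is estimated. It names no exact or penalised method and no rule for zero cells, so ordinary maximum likelihood is the default reading. The sentence that allows simplification on non-convergence stands under the linear mixed model for continuous endpoints. The Wilson method is named for single proportions in the open-label period, not for this comparison.

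A responder must have a lesional score of 0 or 1 "and ≥ 2 -grade improvement from Baseline) at Days 8 and 15". Entry requires a whole-body vIGA-AD "score of Moderate (3) or Mild (2) at Screening" (Protocol section 5.1).

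On size, SAP section 4 states: "The sample size of up to 40 for this study with participants receiving both" treatments. SAP section 3.8 places the interim analysis "when approximately 25 or more of the planned participants have completed the Blinded Period", and section 3.8.1 applies the SAP's methods there as applicable.

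**The concern.** A logistic model whose only term is treatment reproduces the two observed proportions. If one of them is zero, the fitted log odds for that group run to minus infinity, the odds ratio has no finite value, and the printed standard error depends on where the software stopped. The permission to simplify the mixed model would not help even if it were borrowed, because a one-term model has nothing to remove.

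The endpoint is demanding and early. A lesion scored 2 at baseline must clear fully, and a lesion scored 3 must reach 0 or 1, after 7 or 14 days of treatment. With at most 40 placebo lesions, and about 25 at the interim, an empty placebo cell can be foreseen.

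At stake is a promised result that fails in the pattern most favourable to the drug (some active responders, none on placebo). Without a stated rule, the replacement method would be chosen after the zero had been seen, possibly at the unblinded interim.

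**Working it through.** The documents state no response rate, power or effect size for this endpoint, so there is no figure of the plan to reproduce. All rates and counts below are assumptions; the sample sizes (40 and 25) come from SAP sections 4 and 3.8.

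**1. Chance of an empty placebo cell.** With true placebo rate p and n placebo lesions, P(no responder) = (1 − p)^n.

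| Assumed p | n = 40 | n = 25 |
|---|---|---|
| 1% | 0.99^40 = 67% | 0.99^25 = 78% |
| 2% | 0.98^40 = 45% | 0.98^25 = 60% |
| 5% | 0.95^40 = 13% | 0.95^25 = 28% |
| 10% | 0.90^40 = 1.5% | 0.90^25 = 7% |

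The chance exceeds one half only if p is below 1 − 0.5^(1/n), which is 1.7% for n = 40 and 2.7% for n = 25.

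**2. What the model returns.** Take 6/40 active and 0/40 placebo. The odds ratio is (6 × 40)/(34 × 0), which is infinite. A Newton-Raphson fit did not converge:

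- 8 iterations: log odds ratio 7.5, SE 15.8
- 15 iterations: 14.5, SE 522
- 35 iterations: 19.0, SE 4954

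With a single placebo responder (6/40 v 1/40) the fit is well behaved: ln[(6 × 39)/(34 × 1)] = 1.93, SE √(1/6 + 1/34 + 1/1 + 1/39) = 1.1. The failure is therefore specific to the zero cell.

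**3. Pairing alone does not cure it.** A conditional logistic model uses only discordant pairs and fails when no participant responds on placebo alone. With an assumed 15% active rate and independent lesions, that chance is (1 − 0.85p)^40: 50% at p = 2% and 18% at p = 5%.

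**4. What remains available for the odds ratio in 6/40 v 0/40.**

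- The unpaired profile likelihood gives a lower bound of 2.98 and no finite upper limit.
- Six discordant pairs all favouring active give an exact conditional lower bound of L/(1 − L), with L = 0.025^(1/6) = 0.541, that is 1.18. The upper limit is infinite.
- Firth on the unpaired table adds 0.5 to each cell: (6.5 × 40.5)/(34.5 × 0.5) = 15.3, profile 95% CI 1.7 to 2017.

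**5. The difference in proportions.** It is 6/40 − 0/40 = 15 points. With no placebo responder the paired table is fixed: b = 6 participants respond on active only and c = 0 on placebo only. Tango's limits are the values Δ that solve (b − c − nΔ)/√{n[2q + Δ(1 − Δ)]} = ±1.96, where q is the constrained estimate of the placebo-only probability.

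- At Δ = 0.049, q = 0.029 and the ratio is 4.03/2.06 = 1.96.
- At Δ = 0.291, q = 0 and the ratio is −5.63/2.87 = −1.96.

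The matched-pair interval is therefore about 5 to 29 points.

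| 95% CI, points | 6 v 0 of 40 | 4 v 0 of 25 |
|---|---|---|
| Wald | 3.9 to 26.1 | 1.6 to 30.4 |
| Newcombe, unpaired | 3.2 to 29.1 | −0.4 to 34.7 |
| Tango, matched pairs | 4.9 to 29.1 | 0.5 to 34.7 |

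The Wald interval gives the placebo rate no uncertainty, although the Wilson upper limit for 0/40 is 3.84/(40 + 3.84) = 8.8%.

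**The case against.** The strongest reply is that little depends on this odds ratio. Protocol section 9.1 tests no hypotheses, and SAP section 4 calls the study signal seeking. The protocol's main efficacy comparison is TSS change, and it plans only a summary of lesional IGA response. SAP section 3.4 also models the lesional vIGA-AD score as a change at both visits and gives each binary proportion its own interval. The interim may stop the study only for unfavourable signals, and the zero-placebo pattern is favourable. All of this stands and limits the priority.

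Three stronger readings are tempting, and the documents do not support them.

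- **That an empty placebo cell is likely.** No placebo rate is given, and at 10% the chance is 1.5% with 40 participants. The entry score of 2 or 3 is a whole-body score at screening; the lesional baseline distribution is unknown, so the share of lesions that must clear fully is unknown too.
- **That no valid interval would exist.** Only the odds ratio's Wald interval fails. One-sided profile or exact bounds remain, and so does the difference in proportions, which the same sentence promises.
- **That the reported difference would be too tight.** The SAP does not say that the difference is derived from the logistic fit. With 6 v 0 of 40, all three intervals above exclude zero. With 4 v 0 of 25, however, whether zero lies inside depends on the method, which is a reason to name one in advance.

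It is also fair to say that better methods rescue little of the odds ratio: a Firth upper limit of 2017 says almost nothing.

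**Conclusion.** The point holds as a foreseeable gap. Under the default maximum-likelihood reading, a zero placebo cell leaves the promised odds ratio and its Wald interval without usable values, and no fallback applies to this model. This is a realistic possibility, not a shown likelihood. It is more likely than not only if the true placebo rate is below about 1.7% with 40 participants or 2.7% with 25. Exclusions under the 80% compliance rule would move the final analysis toward the smaller-sample figures.

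The difference in proportions survives, but its interval method is unnamed and the model takes no account of the two lesions belonging to one participant. Priority is modest: the endpoint is exploratory, and the TSS comparison and the modelled vIGA-AD score are untouched.

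**What to change.** Amend SAP section 3.4 before the interim unblinding, in the same edit as any correction for pairing:

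- Make the within-participant difference in response proportions (active minus placebo) the main estimate at Days 8 and 15, with a matched-pair score interval, for example Tango.
- Give the odds ratio only by an exact conditional or Firth-penalised method. A Firth fit should use the matched-pair likelihood so that the pairing is kept.
- When a cell is zero, report the odds ratio as a one-sided bound.

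The cost is a few sentences and standard software options. The downside is that in sparse data the odds ratio's upper limit will be infinite or uninformative, and readers will have to rely on the difference.

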	Screening	(at site/home/e staff-admi	d Period ^a study external clinic nistered BID Days 1-14)	(BID dosi	Open-Lab ng at home b	el Period y patient Day	ys 15-42)	End of Study/Early Termination	Safety Follow-up Phone Call
	Days -35	Day 1	Days 2-14	Day 15	Day 18	Day 29	Day 36	Day 43	Day 56
Assessment	to -1	(Baseline)		(+2 days)	(±2 days)	(±2 days)	(±2 days)	(±2 days)	(±2 days)
Prior and concomitant medication review			ongoing from screening					X	X
AE reporting	ongoing	from the time of	of consent (non-tr	reatment- and tr	eatment-emer	gent adverse	events)	X	X

Abbreviations: AE = adverse event; BSA = body surface area; DLQI = Dermatology Life Quality Index; EASI = Eczema Area and Skin Severity Index; ECG = electrocardiogram; FSH = Follicle-stimulating hormone; IGA = Investigator Global Assessment; PK = pharmacokinetic; POEM = Patient-Oriented Eczema Measure; PP-NRS = Peak Pruritus Numeric Rating Scale; SCORAD = SCORing atopic dermatitis; TSS = total sign score; vIGA-AD = validated Investigator Global Assessment-Atopic Dermatitis.

Schedule of Activities (SoA), continued

- a During the Blinded Period, patients will come into the study site twice daily for drug application (approximately 12 hours after the previous dose) and collection of adverse events. The investigational products could be applied by a trained medical professional at patient's home or an external clinic, where available, as a backup option.
- b Procedure performed predose.
- c Procedure performed prior to the morning dose on Day 8.
- d A complete physical examination is to be performed at the Screening and End of Study visits. A symptom-directed physical exam is to be performed as clinically indicated at other visits.
- e A positive urine pregnancy test must be confirmed by a serum test.
- f For post-menopausal women of non-childbearing potential only.
- g On Days 1, 8, and 15, vital signs are measured predose.
- h During the telemedicine visits on Days 18 and 36, drug application, patient questions about daily diary, new or changed AEs, and new or changed concomitant medications will be reviewed with the patient.
- i The vIGA-AD will be conducted predose on all treated lesions at screening, Day 15, 29 and 43 during Open Label period.
- j The lesional PP-NRS will be administered predose separately on each of the 2 target lesions only during Blinded Period and predose at Day 15.

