- The EASI, the POEM, and the DLQI will be performed predose at Baseline (Day 1), Days 15 and 29, and at End of Study/Early Termination visit (Day 43).
- The vIGA-AD (Appendix 4, Section 10.4.2) will be performed, predose at Days 15 and 29, and at End of Study/Early Termination visit (Day 43).
- The SCORAD will be performed predose at Days 15 and 29, and at End of Study/Early Termination visit (Day 43).

- The PP-NRS will be administered daily predose before patient morning application during the Open-Label Period (Days 15-42) and at End of Study/Early Termination visit (Day 43).
- The percentage of treatable BSA will be calculated at Screening, Days 15 and 29, and at End of Study/Early Termination visit (Day 43).

To be included in the population analyzed for efficacy, the patient must have received at least 80% of prescribed study intervention in the Blinded Period and/or at least 80% of prescribed study intervention in the Open-Label Period.

Skin tape stripping (STS) will be performed predose on Days 1, 8 (optional), 15, 29, and at Day 43 for the two target lesions and on Day 1 for the normal skin. For a minimum of 20 patients (may be reduced to 15 patients if there is an impact on enrollment from COVID-19, a 4 or 5 mm punch skin biopsy will be collected from each target lesion on Days 1, 15, and 29 (optional) and from normal skin on Day 1. The lesional biopsy specimens at Days 15 and 29 will be collected in the vicinity of the Day 1 (Baseline lesional sample) biopsy but must be at least 1 cm away from the prior biopsy site. If the target lesion cleared after Day 1 and before Day 15, the biopsy specimen will be taken from the lesional skin location of the target area identified at Baseline.

Additional information regarding study assessments and their timing is located in the Schedule of Activities (Section 1.3).

Inclusive of an up to 5-week screening period, a 6-week treatment period, end of study assessments 1 day after last dose, and a safety follow-up phone call 2 weeks after last dose, the participation will take approximately 13 weeks.

Due to the COVID-19 pandemic, safety measures may be implemented to ensure continued supply of study medication and safety monitoring for patients. When the COVID-19 pandemic resolves, the measures will be repealed back to the previous state as government rules and benefit/risk assessment allow.

As required, these approaches (in accordance with local regulations) will be documented in site guidance materials.

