
Exploratory
 
 Biomarker: To evaluate blood and skin changes in protein expression, lymphocyte infiltration, and epidermal thickness following treatment with PRN473 Gel, 5% at Days 8 and 15 Efficacy: To assess the preliminary efficacy following double-blind treatment with PRN473 Gel, 5% compared to placebo at Days 8 and 15 Efficacy: To assess the preliminary efficacy following open-label treatment with PRN473 Gel, 5% at Days 29 and 43 	
 Biomarker: Change from Baseline in biomarkers using blood samples, skin tape stripping, and skin biopsy 
Efficacy During Blinded Period:
 
 Change from Baseline in lesion TSS at Days 8 and 15 Change from Baseline in daily lesional PP-NRS score up to Day 15 Change from Baseline in lesional validated IGA score at Days 8 and 15 Lesional validated IGA response (proportion of participants with a validated IGA score of 0 or 1 and ≥ 2-grade improvement from Baseline) at Days 8 and 15 
Efficacy During Open-Label Period
 
 Change from Baseline in TSS for the 2 target lesions at Days 29 and 43. 
For EASI:
 
 Percent change from Baseline in EASI at Days 29 and 43 Percent change from Day 15 in EASI to Days 29 and 43 Proportion of patients with EASI 50, EASI 75, and EASI 90 from Day 15 to Days 29 and 43 
For PP-NRS:
 
 Change in PP-NRS from Day 15 to Days 29 and 43 Proportion of participants achieving at least 3-point reduction from Day 15 in PP-NRS at Days 29 and 43 Proportion of participants achieving at least a 4-point reduction from Day 15 in PP-NRS at Days 29 and 43 Change from Day 15 in weekly mean of PP-NRS at Days 29 and 43 
For vIGA-AD:
 
 Proportion of participants achieving at least 2 grade reduction in vIGA-AD to clear (vIGA-AD 0) or almost clear (vIGA-AD 1) from Day 15 to Days 29 and 43 
Other endpoints:
 
 Change from Day 15 in SCORAD at Days 29 and 43 Change from Day 15 in percentage of treatable BSA at Days 29 and 43 Change from Baseline in POEM at Days 15, 29, and 43 Proportions of participants with a reduction in POEM ≥ 4 from Baseline at Days 15, 29 and 43 in participants with POEM ≥ 4 at Baseline Proportions of participants with a reduction in POEM ≥ 4 from Day 15 at Days 29 and 43 in participants with POEM ≥ 4 at Baseline Change from Baseline in DLQI at Days 15, 29, and 43

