Participants with missing data at Baseline will not be included in the analysis. Participants with one or more post-dose timepoints will be included. Mixed model for repeated measures (MMRM) to account for missing data is used for the primary analysis under the missing at random (MAR) framework. Parameters will be estimated using restricted maximum likelihood method with the Newton-Raphson algorithm. Denominator degrees of freedom will be estimated using Kenward-Roger adjustment. All efficacy data after discontinuation of treatment will not be considered.

The same analysis will be conducted for lesional v-IGA-AD score at Days 8 and 15 and lesional PP-NRS. For the other efficacy parameters, only descriptive analyses will be provided.

The weekly average PP-NRS scores will be defined as the average of daily non-missing scores within the week preceding the given visit and will be calculated if there is a minimal amount of 4 non-missing scores.

The POEM score is a 5-point scale: 0 (“No days”), 1 (“1-2 days”), 2 (“3-4 days”), 3 (“5-6 days”) and 4 (“Every day”). The POEM score is calculated by summing the values for the 7 items.

If two or more questions are left unanswered the questionnaire is not scored.

The DLQI is a 4-point scale: 0 (“Not relevant”/“Not at all”), 1 (“A little”), 2 (“A lot”), 3 (“Very much”). For Question 7, “Prevented work or studying” is scored at 3. The DLQI is calculated by summing the score of each question.

The EASI-50/75/95/100 response is defined as a participant achieved a decrease by at least 50%/ 75%/ 95%/100% of EASI from Day 15.

Change in lesional TSS, PP-NRS (daily global and weekly average), EASI, BSA, SCORAD, POEM, DLQI during the Open label period will be analyzed descriptively. Estimations with 95% and 80% CIs may be derived. Sub-score of EASI by localization will also be provided.

Supplemental analyses

Where appropriate, supplemental analyses may be presented excluding observations after administration of rescue medication. No imputation will be made.

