5.4 APPENDIX 4 DATA HANDLING CONVENTIONS

Double blind analysis period is defined from the date of first IMP up to Day15 or date of IMP discontinuation which ever comes first.

Day15 of Open label period is defined as the first day the placebo is not used.

For parameters with evaluations before administration and in cases of rechecked value(s) for one participant, only the last observation will be used as baseline in descriptive statistics and derivations of other parameter values. After baseline, only observations planned in the protocol will be used in descriptive statistics.

For clinical laboratory parameters with non-numeric values, the imputed values used for the descriptive statistics and/or the flags will be determined by considering the following rules:

- If database value is ‘<X’, the value used will be X/2
- If database value is ‘>X’, the value used will be X
- If database value is a range (eg, ‘X – Y’), the values used will be (Y + X)/2

Pharmacokinetic analysis

For ease of presentation, mean values will be arithmetic mean unless specified. Concentration values below the plasma assay limit will be treated as zero in all summary statistics. Mean values below LLOQ will be reported as LLOQ in the tables and not plotted in the figures if after maximal plasma concentration (C_{max}). Mean calculations and their associated statistics will be generated from unrounded numbers and may differ slightly from those values that would be determined using the rounded numbers displayed in the tables. Values expressed in all tables will before ease of presentation and will not be meant to imply accuracy to more than 3 significant figures.

Area under the curve (AUC) values extrapolated by more than 30% will be excluded from any pharmacokinetic statistical analysis.

Analysis windows for time points

The following analysis windows will decide how the scheduled and/or unscheduled visits will be used in the by-visit analyses of efficacy. For participants with premature study discontinuation, follow-up measurements will be reallocated to the corresponding analysis window and reported together with other measurements.

A measurement (scheduled or unscheduled) will be used if it is available and measurement date is within the analysis window.

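### SAP 3.4 gives no computable Day 15 reference for the open-label change in weekly average PP-NRS: at most 3 scores can exist where 4 are required

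*SAP*

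**What the plan says.** Among the open-label PP-NRS endpoints, SAP 3.4 lists "Change in weekly average of PP-NRS from Day 15 to Days 29 and 43". Later in the same section the weekly average is defined as "the average of daily non-missing scores within the week preceding the given visit", and it "will be calculated if there is a minimal amount of 4 non-missing scores". The section also confirms the planned summary: "Change in lesional TSS, PP-NRS (daily global and weekly average), EASI, BSA, SCORAD, POEM, DLQI during the Open label period will be analyzed descriptively". SAP Table 1 and protocol 9.4.3.5 name the endpoint as "Change from Day 15 in weekly mean of PP-NRS at Days 29 and 43".

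On collection, protocol 4.1 and the Schedule of Activities (protocol 1.3) start the whole-patient PP-NRS with the Open-Label Period: daily and predose on Days 15 to 42, plus one score at the Day 43 visit. For the earlier period, footnote j of the Schedule of Activities says: "The lesional PP-NRS will be administered predose separately on each of the 2 target lesions only during Blinded Period and predose at Day 15".

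The Schedule of Activities allows the Day 15 visit 2 days late and none early. SAP Table 6 uses a wider analysis window for Day 15, study days 13 to 18.

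**The concern.** A change in a weekly average needs a weekly average at both ends. At Days 29 and 43 a full week of diary scores lies behind the visit. At Day 15 the diary is only starting, so the week that the rule looks back on falls in the Blinded Period, when the whole-patient score was not collected.

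A programmer who follows SAP 3.4 literally will produce an endpoint with no values for participants seen on schedule. A programmer who wants values must supply a reference that the SAP does not contain. The candidates are different quantities: the single Day 15 score, some combination of the lesional scores, or the first open-label week, which is already on treatment. That choice would be made on open-label data. Those data may also enter the interim analysis, which under SAP 3.8.1 uses the SAP's own methods.

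**Working it through.** The plan states no figure for this, so the check is a count of scheduled scores against the minimum of 4.

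**Inputs**
- Averaging period: the 7 days before the visit; minimum 4 scores (SAP 3.4).
- Days with a daily whole-patient score: 15 to 42 (protocol 4.1 and 1.3).
- Day 15 visit: study days 15 to 17 under the protocol; 13 to 18 in SAP Table 6.
- Day 29 and Day 43 visits: ±2 days under the protocol; 25 to 33 and 39 to 47 in SAP Table 6.

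**Formula.** For a visit on study day v, count the days d from v−7 to v−1 with 15 ≤ d ≤ 42. As a more generous variant, count from v−6 to v, so that the visit day is included.

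**Day 15, with the diary running from calendar Day 15**

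| Visit on study day | Scores strictly before the visit (v−15) | Scores counting the visit day (v−14) | Minimum of 4 met? |
|---|---|---|---|
| 15 | 0 | 1 | no |
| 16 | 1 | 2 | no |
| 17 | 2 | 3 | no |
| 18 (outside the protocol window, inside the SAP window) | 3 | 4 | only if the visit day counts |

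A visit on Day 13 or 14 gives 0 on either count.

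**Day 15, with the diary starting at the visit.** SAP 5.4 states: "Day15 of Open label period is defined as the first day the placebo is not used". If the diary therefore begins at a late visit, the count is 0 before the visit and 1 including it, whatever the day.

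**Lesional scores.** For a visit on Day 15, the preceding week (Days 8 to 14) holds 7 days × 2 lesions = 14 lesional scores. None is a whole-patient score.

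**Days 29 and 43, scores strictly before the visit**
- Day 29 visit on Days 27 to 31: 7 of 7.
- Day 43 visit on Days 41 to 43: 7 of 7. For later visits the last daily score is Day 42, so the count is 42 − (v−7) + 1 = 50 − v. Day 44 gives 6 and Day 45 gives 5.
- Beyond the protocol window but inside the SAP window, Day 46 gives 4 and Day 47 gives 3.

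The minimum is therefore met at Days 29 and 43 throughout the protocol windows. At Day 15 it is not met on any day of the protocol window.

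**The case against.** The strongest counter-argument concerns which score is meant. The other PP-NRS bullets in SAP 3.4 specify the daily global score; the weekly bullet does not, and the definition speaks only of daily scores. If lesional scores counted, the week before Day 15 would not be empty. This stands as a caveat: that the whole-patient score is meant is inferred from the bullet's place under the open-label PP-NRS heading. The inference is a strong one. Protocol 8.1 describes the two as different measures (itch of a lesion against peak itch over the previous 24 hours). In Days 1 to 14 one lesion is on active gel and the other on placebo. The SAP's one averaging over the two lesions is the baseline covariate of the mixed model, which is not a weekly score.

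A reader might also infer that the SAP words this endpoint in two conflicting ways: the Table 1 wording as weekly mean minus the single Day 15 score, and the 3.4 wording as weekly minus weekly. The documents do not support that as the main reading. SAP Table 1 and protocol 9.4.3.5 use the same construction for SCORAD and treatable BSA, where it means the later value minus the Day 15 value of the same measure. Read consistently, both wordings name one quantity and both need the missing reference.

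Finally, it can be said that literal use of the rule produces a visible gap and not a misleading number, and that the daily PP-NRS endpoints cover the same ground. Both are true, and they limit the importance of the point.

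**Conclusion.** The point holds. Under the rule in SAP 3.4, the Day 15 weekly average of the whole-patient PP-NRS, and with it the planned change, is missing for every participant whose Day 15 visit falls in the protocol window. The count is 0 to 2 scores on the literal wording and at most 3 on the most generous one, against 4 required. Neither document gives a special rule for Day 15.

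This rests on two assumptions: the weekly bullet means the whole-patient score, and scores are collected on the scheduled days only. It should not be stretched to say that the value can never exist. A visit on Day 18, with the diary running since calendar Day 15 and the visit day counted, would reach 4. Nor should it be assumed that every Day 43 weekly average is safe: that holds in the protocol window, but a Day 47 visit, still inside the SAP window, has only 3 scores.

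The severity is minor. One exploratory, descriptive, open-label endpoint is affected. The daily PP-NRS change and the 3- and 4-point responder proportions use the single Day 15 score and are unaffected. No primary, secondary or blinded-period result changes.

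**What to change.** Amend SAP 3.4 in one of two ways.

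1. Define the endpoint as the weekly average at Day 29 or Day 43 minus the single predose Day 15 global PP-NRS, and label it so in SAP 3.4 and SAP Table 1. That score is already collected and already anchors the daily-change and responder endpoints. The downside is that a single-day reference is noisier than a 7-day mean, and the two ends of the change are then measured differently, which the label must make plain.
2. Drop the change, and report the Day 29 and Day 43 weekly averages as raw values. The downside is that change from Day 15 is then described by the daily score alone.

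Either way, say that the weekly average refers to the global score, and record the clarification in SAP 3.9, because protocol 9.4.3.5 lists the endpoint. The cost is a sentence or two of SAP text. No new data or procedures are needed.
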